## 2.3 GUIDING CONCEPTUAL FRAMEWORK: THE HEALTH BELIEF MODEL

Many factors contribute to an individual's decision to engage in a health promotion or disease prevention activity. The Health Belief Model (HBM), first developed in the early 1950s, provides an organizing framework to understand people's health behavior decisions. The HBM relies on the assumption that individuals' health decisions stem from a desire to avoid and/or recover from illness and an individual's belief that they can take specific actions to prevent, cure, or reduce the severity of illness. The HBM has been used to assess vaccine hesitancy for other vaccines, including influenza and human papillomavirus (HPV) vaccines. Specific components of the HBM are summarized in Figure 3.

The HBM provides an organizational framework for understanding the considerations of parents and caregivers in deciding whether to vaccinate their children against COVID-19. HBM constructs as applied to parental COVID-19 vaccine decision making include:

1. Perceived susceptibility of their children being infected with SARS-CoV-2.
2. Perceived severity of COVID-19 disease or multisystem inflammatory syndrome in children (MIS-C) in their children.
3. Perceived benefits that their children may experience from receiving a COVID-19 vaccine.
4. Perceived barriers (both attitudinal and logistic) that parents/caregivers may have to obtaining COVID-19 vaccination for their children.
5. Cues to action (personal stories/vignettes, advice, and prompts received from others, including social norms) to trigger a parent/caregiver to vaccinate their children against COVID-19.
6. Self-efficacy or belief in one's own capacity to complete the steps necessary to vaccinate their children against COVID-19 (e.g., identifying a vaccination site, scheduling an appointment, arranging transportation, being able to pay, etc.).

Other individual and community-level factors may influence the above elements, including race, ethnicity, and education level, among others. mHealth vaccine communication apps can address multiple domains of the Health Belief Model simultaneously and hold the potential for customization to incorporate relevant

**Figure 3.** Health Belief Model components.

community, cultural, and/or individual factors, which should improve the effectiveness of the app to increase COVID-19 vaccination rates among app users.

### **mHealth Tools Can Increase Vaccine Confidence and Vaccination Rates**

mHealth tools such as mobile apps and decision support tools demonstrate the potential to positively affect vaccination rates. In an Italian study of a smartphone app to increase parents' knowledge and empowerment when deciding to vaccinate their child against measles, mumps, and rubella (MMR), use of the smartphone app increased parental knowledge and confidence in choosing MMR vaccination and increased parental reported intention to vaccinate. However, actual immunization actions taken after the intervention period were not measured. Similarly, in a cluster-randomized trial of a web-based decision aid for informing parental decision-making about MMR vaccination, the web-based tool, when compared to a leaflet intervention, was associated with lower parental-reported decisional conflict and higher vaccination rates among parents deciding whether to give the first dose of MMR vaccine to their child. A follow-up study of the web-based tool also found it more cost-effective than traditional approaches.

**Cues to action**, which can include behavioral nudges, are a proven effective means of increasing vaccine uptake in various settings. Text messages and voice phone calls can serve as effective prompts to action, and such prompts maximize their impact when they include customized information relevant to the individual recipient. In a large field experiment conducted in the US, text message nudges alone increased flu vaccination rates among 49,000 participants by 5%. Nudges were most effective when they were phrased as there being a vaccine reserved for a participant's child and when they used language that would be expected to come from their healthcare provider.

**Narrative messaging and vignettes** can also serve as prompts to action. Narrative messaging can present information to users in a culturally congruent context and has been shown to increase vaccination rates, particularly in HPV vaccination. A systematic review of educational interventions for increasing HPV vaccination identified two interventional trials that evaluated the impact of narrative stories on vaccination outcomes at up to 2 months. In one study, adolescent participants who viewed narrative videos featuring peers and experts were twice as likely to be vaccinated as those viewing other message formats.

**Tailored messaging, including culturally congruent storytelling**, can provide information to users in a less threatening and more relatable format by using likable characters with similarities to the end-user. Such messaging can engender an emotional connection, which may help persuade individuals to engage in recommended health behaviors. Another example of using narrative interventions to promote vaccine uptake is the CANImmunize app, originally piloted as ImmunizeCA. The CANImmunize app, used in Canada to assist in tracking of vaccination status and to deliver information on vaccines to users, includes video education and personal endorsements for vaccines, combined with push notifications, medical records keeping, and self-directed learning to increase vaccination uptake. Initial reports suggest high usage of the tool, including narrative elements, but controlled trials of the CANImmunize app on vaccination rates are lacking.

**Title:** Improving pediatric COVID-19 vaccine uptake using an mHealth tool: a randomized, controlled trial

**PI:** [name]

In summary, prior research highlights the potential impact of several mHealth interventions to increase vaccine acceptance and uptake. However, findings from these studies may not be directly applicable to COVID-19 vaccination. Prior mHealth-based interventional and large-scale clinical trials assessing the effectiveness of mHealth vaccine-uptake tools are generally lacking. Given that national efforts to use mHealth tools to increase vaccine uptake have been deployed in other countries, establishing an evidentiary base for their effectiveness may have major public health program development and implementation implications. Additionally, prior interventions focus on vaccines that had been licensed through the standard FDA approval process following 10 to 15 years of research and development. By contrast, COVID-19 vaccines are only available to some US age groups under FDA EUA to facilitate the availability of unapproved medical treatments during public health emergencies. EUA for the first COVID-19 vaccines came after an unprecedented 1 year of development and testing. Multiple surveys demonstrate that the newness of these vaccines raises safety concerns for many individuals. Finally, many mHealth interventions lack customization for specific community- and/or individual-level factors that may influence vaccine decision-making, such as race, ethnicity, or geography (such as rurality). Our mHealth Vaccine Uptake app uniquely combines several proven effective methods for increasing vaccination rates with user customization to increase pediatric COVID-19 vaccination rates across diverse settings.

[figure not shown]
## 2.4 EVIDENCE OF CAPABILITY: THE CHILDREN'S COVID-19 STUDENT SYMPTOM CHECKER AND MHEALTH SOFTWARE PLATFORM

The co-Pis of this protocol have extensive experience developing and deploying customizable mHealth clinical decision support apps for healthcare providers. These apps have been used by >50,000 users and incorporate user analytics that enable assessment of engagement with the app. We have also created customizable mHealth apps for COVID-19 infection response decision-making for parents (COVID-19 Student Symptom Checker) that, in partnership with community stakeholders and school districts, have been translated into multiple languages, including Spanish and Nepali (Figure 4).

These apps were built using software and data infrastructure developed at and owned by the University of Nebraska Medical Center (UNMC). The important functionalities of the previous two apps that will also be deployed for the Vaccine Uptake app in the current protocol are:

1. Customization at both the local institution and individual user levels for an experience that is uniquely tailored to each user's local context and personal background.
2. A development environment that enables content viewing in multiple languages.
3. A content management interface that enables rapid content modification and updates.
4. Push notifications to participants to trigger app usage.
5. Back-end analytics to measure user interactions with app components.

Further details of the functionality of our mHealth tool are outlined in Section 8 below.

[figure not shown]

**Figure 4.** Screenshot of the Children's COVID-19 Student Symptom Checker.

Preliminary data since release of the COVID-19 Student Symptom Checker app in August 2020 shows that these tools demonstrate broad uptake and use across diverse racial and ethnic backgrounds, with more than 85% of eligible households having registered for the tool. The median weekly number of students screened by the app was 7,000 (Figures 5a & b). User feedback demonstrated that parents used the app to make decisions on whether to obtain SARS-CoV-2 testing and whether to send their children to school. Feedback from school districts showed that school nurses and principals used the app to help them counsel parents regarding school attendance and to review components of school response plans included within the app.

Finally, members of our team have experience developing and testing the effectiveness of vaccine communication interventions. Specifically, [name] has assessed the impact of text messaging interventions on HPV vaccination rates; conducted prospective clinical trials of multi-modal, clinic-based interventions to increase HPV vaccination rates; and assessed parental perceptions of barriers to vaccination through the Pediatric Research in Outpatient Settings (PROS) Network, a national practice-based research network.

[figure not shown]
In summary, our team has the expertise in mHealth tool development and deployment, clinical trials conduct, and vaccine communication to conduct the proposed study.

**Figure 5a.** Sample dashboard of enrollment metrics generated from data provided by users of the Student Symptom Checker.

**Title:** Improving pediatric COVID-19 vaccine uptake using an mHealth tool: a randomized, controlled trial

**PI:** [name]

**Figure 5b.** Sample dashboard of enrollment metrics generated from data provided by users of the Student Symptom Checker.

### **3. RISK/BENEFIT ASSESSMENT**

#### **3.1 KNOWN POTENTIAL RISKS**

This study poses minimal risk to participants (see definition of participants in Abbreviations & Definitions). Participants (in both the Vaccine Uptake app and General Health app arms) will provide protected health information (PHI) (e.g., children's names, dates of birth, and dates of vaccination) to the study team. While the study team will make every effort to store this electronic information in secure electronic databases and physical documents in secure facilities, there remains a risk of accidental as well as mandated disclosure of PHI.

Participants will view content and answer questions related to the COVID-19 pandemic that may provoke some emotional stress or anxiety relating to the pandemic and/or COVID-19 vaccination.

The study will expose participants to content providing guidance in accordance with the most current recommendations from the CDC/ACIP. This information is subject to change. While educational content for both arms will undergo revisions in real time, participants may not always choose to access updated information after the study team posts it. In addition, app content will likely recommend vaccination with the COVID-19 vaccine while it is still available under FDA EUA rather than FDA approval for some of the participants based on their age.

#### **3.2 KNOWN POTENTIAL BENEFITS**

Participants who receive the Vaccine Uptake app will receive self-directed, multi-format education on the COVID-19 vaccine, which may reduce participant stress and/or anxiety in decision making regarding whether their child should receive the COVID-19 vaccine and increase their knowledge about vaccination.

Caregiver participants who receive the Vaccine Uptake app will receive information on local resources for vaccinating their children against COVID-19, which may result in increased vaccination uptake among participants' children.

Caregiver participants who receive the General Health app will receive general health and infection prevention education, which may improve their own knowledge and risk reduction behaviors, which may decrease their own, and their children's risk of contracting an infection and suffering the negative consequences from the infection.

There is also potential for benefit to other parents and their children in the future if the study demonstrates that the intervention provides an effective means of educating parents about and increasing pediatric uptake of COVID-19 vaccine.

#### **3.3 ASSESSMENT OF POTENTIAL RISKS AND BENEFITS**

We do not anticipate significant health risks to participants and will make every effort to minimize the possible risks described in Section 3.1. The benefit of understanding the effect of a vaccine-education mHealth tool on

**Title:** Improving pediatric COVID-19 vaccine uptake using an mHealth tool: a randomized, controlled trial

**PI:** [name]

promoting pediatric COVID-19 vaccination uptake outweighs the risks. Standards of medical care provided to participants' children will not be altered based on participants' study-related activities.

This protocol minimizes risks to participants by (a) correctly and promptly informing participants about risks (Section 3.1, above) so that they can join in partnership with the researcher in recognizing and reporting harms; (b) having staff properly trained in administering study procedures that may cause psychological distress, such as survey administration; and (c) providing safety monitoring.

If the FDA issues new warnings or precautions or withdraws EUA/approval for any of the COVID-19 vaccines for any of the included pediatric age groups during the study, the study team will take responsive action. Actions will include prompt notification of participants via at least one of the following methods: app push notification, text message, phone call, email, registered mail, as well as possibly study termination depending on the severity of the concern, as determined by the PIs and data safety monitoring board (DSMB).

#### 4. OBJECTIVES AND ENDPOINTS

OBJECTIVES	ENDPOINTS	JUSTIFICATION FOR ENDPOINTS
Primary		
Objective 1: Determine the effect of a parent-facing, vaccination decision-making mHealth tool on children's COVID-19 vaccine series completion	Proportion of children who complete COVID-19 vaccination, as verified in state, clinic, or participant-held records	The intended goal of the intervention is to increase the number of children receiving a complete COVID-19 vaccine series since series completion provides children with maximal protection afforded by vaccination. Self-report of vaccination will not be used, only verified vaccination records, to avoid introduction of recall and social desirability biases in the assessment of the endpoint. The study team will define vaccine series completion as per the current Advisory Committee on Immunization Practices (ACIP) guidance for the vaccine product. For children who receive a product that requires more than 2 doses for the primary series, receipt of up to 3 doses will be considered complete.
Secondary		
Objective 1: Determine the effect of a parent-facing, vaccination decision-making mHealth tool on children's	Proportion of children who receive ≥1 dose of the COVID-19 vaccination series, as	Some COVID-19 vaccines require completion of a multiple-dose series to achieve intended immunity. A necessary precursor to our primary endpoint of vaccine series completion is vaccine

**Title:** Improving pediatric COVID-19 vaccine uptake using an mHealth tool: a randomized, controlled trial

**PI:** [name]

OBJECTIVES	ENDPOINTS	JUSTIFICATION FOR ENDPOINTS
COVID-19 vaccine series initiation	verified in state, clinic, or participant-held records	series initiation (i.e., receipt of first dose). As more individuals initiate vaccine series than complete it, vaccine series initiation may be a more sensitive indicator of the intervention's effect.
Objective 2: Determine the effect of a parent-facing, vaccination decision-making mHealth tool on parental attitude toward pediatric COVID-19 vaccination	Change in enrolled parent/caregiver domain scores from baseline to week 16 on the modified SAGE Vaccine Hesitancy Scale adapted for the COVID-19 Vaccine	Vaccine hesitancy contributes to vaccination decisions. Measuring any changes in vaccine hesitancy in association with use of the Vaccine Uptake app will provide further insight into the impact of the app on parent/caregiver decision-making.

## 5. STUDY DESIGN

### 5.1 OVERALL DESIGN

This multi-site, parallel, randomized, controlled trial will assign parents/caregivers of children eligible to receive COVID-19 vaccine seen at participating clinics to receive either the mHealth Vaccine Uptake app or the General Health app containing general infection and child health topics. Randomization will be stratified by site using a permuted block design with varying block size. Outcome is receipt of COVID-19 vaccine by the parents'/caregivers' children.

[figure not shown]
### 5.2 SCIENTIFIC RATIONALE FOR STUDY DESIGN

**Rationale for a randomized trial:** Based on the Health Belief Model and prior evidence, factors contributing to individuals' vaccine hesitancy, confidence, and/or refusal likely are multi-factorial and vary widely across individuals. Randomization of participants to the Vaccine Uptake or the General Health app study arms, outlined further below, is designed to minimize selection bias of individuals with specific attitudes or beliefs into a single study arm. For example, individuals who have lower vaccine hesitancy may be at baseline more interested/open to participating in the Vaccine Uptake study arm, whereas individuals with greater hesitancy may be more likely to decline. This potential bias ideally will be minimized by having participants consent to engaging in whatever study arm to which they are randomly assigned.

**Rationale for using the mHealth app platform developed at UNMC in the intervention and control study arms:** Most parents/caregivers, including those in rural areas, have access to a mobile device and the internet (see Section 2.1, Background). Prior studies support the feasibility of deploying app-based interventions aimed at increasing vaccination rates. Based on community feedback and our team's experience deploying app-based interventions for COVID-19 symptom screening, ensuring that the app imposes a low data burden is important

to maximizing uptake. Consequently, the platform developed at the UNMC uses data at only four time points: 1) initial download/registration (approximately 200-300 megabytes), 2) recording of sessions (2-3 kilobytes/session), 3) push notifications (2-3 kilobytes/notification), and 4) periodic updates (20-30 kilobytes/update). Thus, our mHealth app platform incurs a very low data demand, which minimizes the barrier to use for participants.

**Rationale for use of a control mHealth app:** Participants in the General Health app arm will receive access to an mHealth app to ensure similarity in access to intervention materials (e.g., sending out of a link to register for app access via the same platforms) and barriers to access (e.g., low technology literacy, lack of an internet-capable device). The goal is to compare the impact of the customized, targeted content over generic information on an app, not the ability to access content on an educational app.

**Figure 6.** Comparison of functional and content elements of the Vaccine Uptake app and General Health app.

**Title:** Improving pediatric COVID-19 vaccine uptake using an mHealth tool: a randomized, controlled trial

**PI:** [name]

**Limitations of using a mHealth control:** App content, even if not customized or vaccine-related, may still elevate vaccination rates above what they would be with no intervention due to reducing barriers to accessing general information about infection control and prevention.

### 5.3 END OF STUDY DEFINITION

The study will end for the participant after they have reached 29 weeks of enrollment and either completed their 24-week assessment or failed to complete it by week 29.

## 6. STUDY POPULATION

### 6.1 INCLUSION CRITERIA

#### 6.1.1 PARTICIPANTS

For this study, there will be two sets of inclusion/exclusion criteria:

1. Parents/caregivers who will receive either the Vaccine Uptake app or General Health app
2. Children of the above-mentioned parents/caregivers who are eligible to receive COVID-19 vaccine in their state

#### Parent/caregiver inclusion criteria:

- Age of majority, as defined by the state of residency
- Access to a mobile device that can store and run the study app for 24 weeks. Devices that can run the app include mobile phones and tablets running Android or iOS operating systems
- Able to speak and read in English or Spanish
- Be a parent/caregiver with primary medical decision-making and legal authority to consent to vaccination decisions for at least one child who meets the child inclusion criteria

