#### Child inclusion criteria:

- Age 6 months to less than age of majority, as defined by the child's state of residence
- Has not received any doses of COVID-19 vaccine based on parent/caregiver report
- Eligible to receive COVID-19 vaccine
- Patient at a participating clinic

**Rationale for parent/caregiver inclusion criteria:** Parent/caregiver vaccine confidence/acceptance will vary widely, ranging from those who firmly refuse the COVID-19 vaccine to those who strongly endorse the COVID-19 vaccine for their children. All parents/caregivers, regardless of baseline vaccine hesitancy/confidence, are eligible to participate in the study. Subject randomization is intended to balance the proportion of vaccine refusing/vaccine endorsing participants. Parental vaccine hesitancy will not be assessed prior to enrollment. Such assessment may bias enrollment towards those individuals with greater vaccine acceptance through social

**Title:** Improving pediatric COVID-19 vaccine uptake using an mHealth tool: a randomized, controlled trial

**PI:** [name]

desirability bias. Unlike vaccine-hesitant individuals, baseline vaccine refusing parents/caregivers are unlikely to be willing to participate in vaccine communication efforts and, therefore, will likely decline study participation during recruitment or informed consent.

Due to evolving COVID-19 EUAs by age categories and variable availability of vaccine by state, the study team may rescreen parents who do not meet enrollment criteria at initial screening.

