#### **WEEK 8 ASSESSMENT**

**At the week 8 time point**, the caregiver participants will be sent a link to an assessment that asks for the following topics:

1. Vaccine status of eligible children

The surveys will ask caregiver participants for the dates, brands, and administrators for all COVID-19 vaccinations that any of their children received since enrollment, if any. For each vaccinated child, the survey will ask participants to upload a photo of the vaccination card. If a participant is unable to upload the photo or the writing on a card is illegible, the enrolling site personnel will contact the participant to schedule a time for a video conference to view and verify the card information.

2. Usability of the app

Surveys will include a systems usability assessment measured by the System Usability Scale (SUS). The SUS is a simple, ten-item scale giving a global view of subjective assessments of usability. SUS instructions will ask caregiver participants to record their immediate response to each item, rather than thinking about items for a long time. Responses range from Strongly Agree to Strongly Disagree. The SUS yields a single number representing a composite measure of the overall usability of the system. SUS scores have a range of 0 to 100, with 100 representing a perfect score.

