In determining sample size, each caregiver is considered to be a cluster with an average of 2 unvaccinated children. To demonstrate an improvement in the proportion of unvaccinated children of caregivers who complete the COVID-19 vaccination series due to the mHealth intervention from 30% to 40% would require 758 caregivers (379 per arm), at the two-sided 0.05 significance level with power of 0.90 and an intraclass correlation coefficient of 0.60. The table below shows the sample size needed to have 90% power to detect a 10-percentage point increase in the proportion of children who complete the vaccination series using the Vaccine Uptake app with varying levels of intraclass correlation. To ensure that there are at least 758 caregivers, the primary analysis population, we expect to randomize 892 caregivers to account for up to 15% of randomized participants who do not use the Vaccine Uptake app or General Health app after downloading it during enrollment.

Intraclass Correlation Coefficient	Sample Size
0.40	331 per arm (662 total)
0.50	355 per arm (710 total)
0.60	379 per arm (758 total)
0.70	402 per arm (804 total)
0.80	426 per arm (852 total)

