6.2 ANALYSIS OF THE PRIMARY EFFICACY ENDPOINT

For the primary efficacy measure, we will test the following null hypothesis:

H₀: Vaccination series completion rate among children of caregivers assigned to the Vaccine Uptake app will not differ from the vaccine series completion rate among children of caregivers assigned to the General Health app

vs

H₁: Unvaccinated children of caregivers assigned to the Vaccine Uptake app will be more likely to achieve COVID-19 vaccine series completion than those children whose caregivers are assigned to the General Health app

For each vaccine-eligible child, the primary endpoint will be whether or not the child initiates and completes the COVID-19 vaccine series during the 24 weeks of the intervention period. The study team will define vaccine series completion as per the current ACIP guidance for the vaccine product. For children who receive a product that requires more than 2 doses for the primary series, receipt of up to 3 doses will be considered complete. Vaccine doses will only be valid for study purposes if given within the 24 weeks of study participation. Additional doses, when required for primary series completion, will only be valid if they are in accordance with ACIP-recommended interval minus a 4-day grace period, in accordance with recommendations of the ACIP. Also, per ACIP, there will be no maximum interval between valid doses. Incorrect second vaccine product (i.e., mixed series) will be invalid for study purposes.

Univariate Analysis

The primary endpoint will be collected as a dichotomous variable (yes/no). We will report the probability of COVID-19 vaccine series completion for each intervention group (Vaccine Uptake app vs General Health app). Initially, an unadjusted non-modeling approach using SAS PROC FREQ will be used estimate the relative risk (RR) for COVID-19 vaccine series completion (with Wald 95% CI), with the General Health app intervention group as the reference group. The analysis will be performed for all three populations (ITT, mITT, and PP).

Primary and Multivariable Analysis

A mixed-effect Poisson regression with robust error variance will be used to report adjusted relative risk (RR) with 95% CI accounting for site random effect and controlling for clustering by caregiver. The multivariable model will allow adjustment for covariates. The analysis will be performed for all three populations (ITT, mITT, and PP).

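### Decision authority is required for only one child per caregiver and is not recorded per child, yet every vaccine-eligible child counts in the completion and initiation endpoints

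*Protocol*

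**What the plan says.** Protocol 6.1.1 places authority among the caregiver criteria. The caregiver needs "primary medical decision-making and legal authority to consent to vaccination decisions for at least one child who meets the child inclusion criteria". Authority is thus treated as something separate from the child criteria, and one child satisfies it. The same section describes the second population as "Children of the above-mentioned parents/caregivers who are eligible to receive COVID-19 vaccine in their state".

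The child inclusion list has four items: age, no earlier dose ("Has not received any doses of COVID-19 vaccine based on parent/caregiver report"), vaccine eligibility and being a patient at a participating clinic. The child exclusion list in 6.2.1 has six. None asks whether the enrolled caregiver may consent to vaccination of that particular child.

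Data collection follows the whole family. The enrolment survey (7.5.1) takes details of the participant's children, and the week 8 assessment (7.5.3) asks about "all COVID-19 vaccinations that any of their children received since enrollment, if any". Neither these sections nor Table 1 lists an item on authority per child.

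SAP 6.2 then states: "For each vaccine-eligible child, the primary endpoint will be whether or not the child initiates and completes the COVID-19 vaccine series". Protocol 11.4.2 defines the primary endpoint in the same way, and protocol 11.4.3 and SAP 6.3.1 define initiation per vaccine-eligible child too. In the sample size calculation (protocol 11.2, SAP 3.3), "each caregiver is considered to be a cluster with an average of 2 unvaccinated children".

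**The concern.** The intervention works on the enrolled caregiver's decision. Suppose a caregiver has authority for one child but someone else decides on vaccination for a sibling. If the sibling meets the child criteria, the sibling is counted even when vaccine-eligible is read strictly, as meeting every item on both child lists. The app can reach that child only if its content is passed on to the person who does decide.

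The sample size applies the 10-point effect to all counted children. Counted children who respond less would pull the relative risk towards 1 and reduce power, for completion and for initiation. The mITT and PP populations would not remove them, because both are defined by the caregiver's app use and retention (protocol 11.3, SAP 5.3). With nothing recorded per child, the analysts could neither exclude these children nor measure how many there are.

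**Working it through.** **Inputs from the documents.** 30% versus 40%, two-sided 0.05, power 0.90, 2 children per caregiver, ICC 0.60, 758 caregivers needed and 892 randomised (protocol 11.2); 1:1 allocation of caregivers (8.3); ITT as the primary population (11.3).

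**Assumed.** The share f of counted children outside the enrolled caregiver's authority is not in the documents, so a range is shown.

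**Step 1: reproduce the plan.** Two proportions, unpooled variance:

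- Children per arm without clustering: (1.960 + 1.282)² × (0.30×0.70 + 0.40×0.60) / 0.10² = 472.8.
- Design effect: 1 + (2 − 1) × 0.60 = 1.6.
- Caregivers per arm: 472.8 × 1.6 / 2 = 378.3, rounded up to 379, or 758 in total.
- Inflation: 758 / 0.85 = 891.8, rounded up to 892, or 446 per arm.

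The same formula matches all five rows of the ICC table. The sample size has no arithmetic error.

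**Step 2: diluted effect.** If the app has no effect in the share f, the intervention-arm rate is p₂ = 0.30 + 0.10 × (1 − f). The effective number of children per arm is n = caregivers × 2 / 1.6, which is 473.75 at 379 per arm and 557.5 at 446. Power = Φ{ (p₂ − 0.30) / √[(0.21 + p₂(1 − p₂)) / n] − 1.96 }.

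Example, f = 10% at 379: p₂ = 0.39, standard error √(0.4479 / 473.75) = 0.03075, and 0.09 / 0.03075 − 1.96 = 0.967, so power is 83.3%.

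| f | Difference (points) | RR = p₂/0.30 | Power, 379 per arm | Power, 446 per arm |
|---|---|---|---|---|
| 0 | 10.0 | 1.33 | 90.1% | 94.1% |
| 5% | 9.5 | 1.32 | 87.0% | 91.7% |
| 10% | 9.0 | 1.30 | 83.3% | 88.8% |
| 15% | 8.5 | 1.28 | 79.0% | 85.1% |

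**Step 3: partial sharing.** If half the effect reaches these children, power at f = 5%, 10% and 15% is 88.6%, 87.0% and 85.2% at 379 per arm, and 93.0%, 91.7% and 90.4% at 446.

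**Step 4: cost of restricting the endpoint.** Counting only children under the caregiver's authority restores the 10-point effect but lowers the mean cluster size to m = 2(1 − f), with n = caregivers × m / (1 + 0.60(m − 1)).

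- 379 per arm: 89.7% (f = 5%) and 89.3% (f = 10%), against 90.1%.
- 446 per arm: 93.8% and 93.5%, against 94.1%.

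The loss is between 0.3 and 0.8 points.

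**The case against.** **The group may hardly exist.** The synopsis (protocol 1.1) describes the population as custodial parents and caregivers. A counted child must also be the participant's own, unvaccinated, eligible and a patient at a participating clinic. Shared custody does not by itself remove the enrolled caregiver's authority. This stands: f may be near zero, and nothing in the documents supports a particular value.

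**The protocol explains its choice.** The rationale in 6.2.1 says that several caregivers may hold authority for a child, that the outcome is the child's completion rather than one parent's decision, and that information will probably be shared with another decision-maker. This stands in part. It answers the case of shared authority and makes a nil effect less likely. It does not address a sibling for whom the enrolled caregiver has no authority.

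**The ITT sample has room.** With all 892 analysed, power stays at or above 90% up to f of about 8% with no effect in these children, and up to f = 15% with half the effect. A reader might infer that power must fall below the stated 90%; for small f that is not shown. The room is not free, however. It was added for up to 15% of participants who do not use the app, and ITT counts them too. If they also show no effect (an assumption), the difference is 8.5 points at f = 0 and 0.85 × 9.0 = 7.65 points at f = 10%, giving power of 85% and 77% at 446 per arm.

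**No confounding.** A reader might infer a biased comparison between arms. Randomisation is by caregiver, so such children are expected equally in both arms. The possible result is attenuation and lost power.

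**Conclusion.** The gap in the text is real: authority is tested once per caregiver, not tested or recorded per child, and the endpoints count each vaccine-eligible child. That all of a caregiver's eligible children count is the natural reading of the endpoint, although the documents do not say it in those words. The consequence is conditional. With no effect in such children, an assumed f of 5% to 10% costs about 3 to 7 points of power at 379 per arm and about 2 to 5 points at 446. These are worst cases, since some information may be passed on.

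Two further readings go beyond the documents:

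- **Ageing out.** The child criterion reads "Age 6 months to less than age of majority, as defined by the child's state of residence", so a child may reach majority during follow-up, and a reader might want such children excluded. They are under the caregiver's authority until that date. Any estimate of their number needs an age distribution the documents do not give and a majority age they leave to each state. Excluding them would also remove the oldest adolescents, the age band with the highest uptake in protocol Table 5. That is a trade-off, not a correction.
- **Permission for record review.** Child assent is waived (7.4), and a reader might infer that no other permission covers a child outside the caregiver's authority. That cannot be checked, because the consent pages are not among the documents reviewed.

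**What to change.** 1. Add one item to the child inclusion criteria in protocol 6.1.1: the enrolled caregiver is the main medical decision-maker for this child and is legally able to consent to the child's vaccination.
2. Record it as one yes/no per child in the enrolment survey (7.5.1), before randomisation, so that the answer cannot depend on the arm.
3. In protocol 11.4.2 and 11.4.3 and SAP 6.2 and 6.3.1, state that the counted children are those with a yes.

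At minimum, keep the present denominator, record the item, and pre-specify a sensitivity analysis of both endpoints restricted to children with a yes.

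The cost is one criterion, one survey item and one sentence per analysis section. A few siblings leave the denominator, which takes under 1 point of power at f of 10% or less. The item would also show what f is.
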